8.2. Setting

8.2.1. **Redacted**

Redacted is derived from records of 150,000 healthcare providers in the United States, that include more than 2000 hospitals and 7000 clinics; treating more than 103 million patients receiving care as of January 2020. The data is certified as de-identified by an independent statistical expert following Health Insurance Portability and Accountability Act (HIPAA) statistical de-identification rules, and managed according to **Redacted** customer data use agreements.^{18,19} Clinical, claims and other medical administrative data is obtained from both Inpatient and Ambulatory EHRs, practice management systems and numerous other internal systems. Information is processed, normalized, and standardized across the continuum of care from both acute inpatient stays and outpatient visits. **Redacted** data elements include: demographics, medications prescribed and administered, immunizations, allergies, lab results (including microbiology), vital signs and other observable measurements, clinical and inpatient stay administrative data and coded diagnoses and procedures. In addition, **Redacted** uses natural language processing (NLP) computing technology to transform critical facts from physician notes into usable datasets. The NLP data provides detailed information regarding signs and symptoms, family history, disease related scores (ie, RAPID3 for RA, or CHADS2 for stroke risk), genetic testing, medication changes, and physician rationale behind prescribing decisions that might never be recorded in the EHR.

RedactedRedacted
RedactedRedactedRedactedRedactedRedactedRedactedRedactedRedacted
Redacted
Redacted

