History of serious infections	Baseline Characteristic	Hospitalized infections within baseline period
Malignancy	Baseline Characteristic	Diagnosis of malignancy within baseline period
Pregnancy	Baseline C haracteristic	Diagnosis of pregnancy within baseline period
Interstitial lung disease (ILD)/COPD/Asthma	Baseline Characteristic	Diagnosis of ILD/COPD/Asthma within baseline period
Venous thromboembolism (VTE)	Baseline Characteristic	Diagnosis of pulmonary embolism (PE) or deep vein thrombosis (DVT) within baseline period
Heart disease (HD)	Baseline Characteristic	Diagnosis of HD (heart failure, hypertensive heart disease, pulmonary heart disease, valvular disorders, arrhythmia, congenital

RedactedRedacted
RedactedRedactedRedactedRedactedRedactedRedactedRedactedRedactedRedacted
Redacted
Redacted

Variable	Role	Operational definition ^a
		heart disease) within baseline period
History of cerebrovascular accident (CVA)	Baseline Characteristic	History of ischemic or hemorrhagic stroke within baseline period
Peripheral vascular disease (PVD)	Baseline Characteristic	Diagnosis of PVD within baseline period
Other immune deficiencies	Baseline Characteristic	Diagnosis of immunodeficiency within baseline period
Human immunodeficiency virus (HIV)/AIDS	Baseline Characteristic	Diagnosis of HIV/AIDS within baseline period
Diabetes	Baseline Characteristic	Diagnosis of diabetes within baseline period
Chronic kidney disease (CKD)/Dialysis	Baseline Characteristic	Diagnosis of CKD or dialysis procedure during baseline period
Liver Disease	Baseline Characteristic	Diagnosis or procedure during baseline period
Corticosteroid Use	Baseline Characteristic	Prescription during baseline period for systemic corticosteroids
Influenza Season	Stratifying variable	Annually June 1 st – May 31 st 2014-2015; 2015-2016; 2016-2017; 2017-2018; 2018-2019
Influenza	Primary Endpoint	Clinical diagnosis of influenza
ILI	Primary Endpoint	Clinical diagnosis of ILI
Influenza vaccine	Secondary Endpoint	Yes/No, evidence of influenza vaccine corresponding to seasons: 2014-2015; 2015-2016; 2016-2017; 2017-2018; 2018-2019 This will only be reported for each influenza season
Influenza Complications - Pneumonia	Secondary Endpoint	Clinical diagnosis of pneumonia on or up to 30 days after an influenza diagnosis
Influenza Complications - Stroke or myocardial infarction (MI)	Secondary Endpoint	Clinical diagnosis of stroke or MI on or up to 30 days after an influenza diagnosis

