Influenza Complications – Neurological Disorder	Secondary Endpoint	Clinical diagnosis of neurological disorder on or up to 30 days after an influenza diagnosis

RedactedRedacted
RedactedRedactedRedactedRedactedRedactedRedactedRedactedRedactedRedacted
Redacted
Redacted

Variable	Role	Operational definition ^a
Corticosteroid Use	Secondary Endpoint	Corticosteroid use within 30 days [-30,30] around an influenza diagnosis
Methotrexate Use	Secondary Endpoint	Methotrexate use within 30 days [-30,30] around an influenza diagnosis
Azathioprine Use	Secondary Endpoint	Azathioprine use within 30 days [-30,30] around an influenza diagnosis
Influenza Hospitalization	Secondary Endpoint	Yes/No: hospitalization within 30 days post influenza diagnosis
In-hospital death	Secondary Endpoint	Death that happened during influenza hospitalization
Death	Secondary Endpoint	Death within 90 days post influenza diagnosis

a. Where applicable codes and other definitions to be further defined in the SAP.

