8.7. Data Analysis

Detailed methodology will be documented in a SAP, which will be dated, filed and maintained by the sponsor. The SAP may modify the plans outlined in the protocol; any major modifications of primary endpoint definitions or their analyses would be reflected in a protocol amendment. Descriptive analysis will be performed for this study. Baseline demographics, comorbidities and clinical characteristics will be analyzed using baseline data for RA, PsA and UC patients, then stratified by index treatment group, and age (<65 and 65 and older). Means, medians, and standard deviations will be provided for continuous variables. Counts and percentages will be provided for dichotomous variables or categorical variables.

RedactedRedacted
RedactedRedactedRedactedRedactedRedactedRedactedRedactedRedacted
Redacted
Redacted

The frequency and incidence rates for influenza and influenza like illness, the frequency of influenza complications, influenza-related hospitalization and mortality among patients treated for RA, PsA, and UC in subsets of patients defined by different index treatments will be reported stratified by age (<65 and 65 and older).

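### Influenza hospitalization leaves day 0 and stays already in progress out of its stated window, and counts admissions for any cause although it is reported as influenza-related

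*Supplement*

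**What the plan says.** All the definitions are in the variable table of protocol Section 8.3.

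- Influenza hospitalization, a secondary endpoint: "Yes/No: hospitalization within 30 days post influenza diagnosis".
- In-hospital death, a secondary endpoint that depends on it: "Death that happened during influenza hospitalization".
- Pneumonia complication: "Clinical diagnosis of pneumonia on or up to 30 days after an influenza diagnosis". The stroke or MI row and the neurological row use the same window.
- Corticosteroid use: "Corticosteroid use within 30 days [-30,30] around an influenza diagnosis". The methotrexate and azathioprine rows use the same window.
- The anchoring event is a "Clinical diagnosis of influenza", with no restriction to outpatient care.

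Section 8.2 describes the source: "Clinical, claims and other medical administrative data is obtained from both Inpatient and Ambulatory EHRs". Section 8.7 plans to report "the frequency of influenza complications, influenza-related hospitalization and mortality among patients treated for RA, PsA, and UC", by index treatment and by age under 65 against 65 and older. Section 8.3 and the footnote to its table leave code lists, time periods and further definitions to the SAP.

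**The concern.** A patient may be admitted with a respiratory illness and have influenza recorded only once in hospital. If the window is applied to the admission date, that stay began before the diagnosis and does not qualify. A death during the stay then drops out of in-hospital death as well, because that endpoint needs a qualifying hospitalization first.

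The second problem runs the other way. Nothing in the definition links the stay to influenza, so a planned admission for another reason some weeks after a mild influenza episode counts as an influenza hospitalization, and a death during it counts as in-hospital death.

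Hospitalization and in-hospital death are two of the study's main measures of severity. A reader will take them as describing how often influenza put these patients in hospital and how often they died there. As printed, the definition supports neither statement cleanly.

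**Working it through.** The plan gives no rate, sample size or expected frequency for this endpoint, so there is no figure to reproduce. The check is a comparison of wording, followed by test cases.

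**Step 1: windows in the same table, with day 0 as the diagnosis date**

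| Row | Day 0 stated? | Days before diagnosis stated? |
|---|---|---|
| Pneumonia, stroke or MI, neurological | Yes | No |
| Corticosteroid, methotrexate, azathioprine | Yes | Yes, to day −30 |
| Influenza hospitalization | No | No |

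The table states day 0 or earlier days in six rows. The hospitalization row says only *post*, and does not say whether the window applies to the admission date or to any day of the stay.

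**Step 2: three possible readings**

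- (a) Admission falls after the diagnosis date, days 1 to 30.
- (b) Admission falls on days 0 to 30.
- (c) Any hospital day falls within the 30 days after diagnosis.

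**Step 3: test cases (hypothetical)**

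| Case | (a) | (b) | (c) |
|---|---|---|---|
| 1. Admitted day −1, influenza recorded day 0, dies in hospital day 4 | No | No | Yes |
| 2. Admitted and diagnosed on day 0, discharged day 3 | No | Yes | Yes |
| 3. Diagnosed as an outpatient, admitted with influenza pneumonia day 3 | Yes | Yes | Yes |
| 4. Diagnosed as an outpatient, unrelated elective admission day 25 | Yes | Yes | Yes |

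In-hospital death follows the same columns. The death in case 1 counts only under (c). A death during the stay in case 4 would count under all three.

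Two conclusions follow. The loss of in-progress stays depends on the reading: it occurs under (a) and (b) and largely disappears under (c). The inclusion of unrelated stays does not depend on the reading.

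**Step 4: direction of the error**

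Let p be the true share of influenza patients hospitalized for influenza, h the share of those whose stay is not counted, and u the share of all influenza patients counted only because of an unrelated stay. Then

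reported share = p × (1 − h) + u.

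The reported share is too low if u < p × h and too high if u > p × h. The documents give none of p, h or u. As an illustration under assumed values only, take p = 10%. With h = 20%, p × h = 2 percentage points, and with h = 50%, p × h = 5 percentage points. An unrelated-admission share above those values would reverse an undercount into an overcount.

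**The case against.** The strongest reply is that the row is provisional. Section 8.3 and its footnote leave time periods and codes to the SAP, and the amendment log indicates that the SAP covers these endpoints. Day 0 and the admission-date rule are details that a SAP commonly settles. This stands as a limit: the protocol shows an unspecific definition, not a proven error in the analysis. It does not dispose of the point. The protocol has already printed a window for this endpoint that differs from its neighbours, and Section 8.7 promises an amendment only for major changes to the primary endpoints, so a correction made in the SAP could leave the protocol text as it is.

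A second reply is that the text never mentions the admission date. Reading (c) is possible, and the documents do not say whether an inpatient diagnosis is dated to admission, encounter or recording. The 90-day death row also uses *post*, which suggests the word may have been chosen loosely. All of this stands. Exclusion of in-progress stays is the literal reading, not the only one.

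Third, severe cases are not lost from the study. The complication endpoints run from day 0 in any setting, and death within 90 days does not depend on hospitalization. That is correct and limits the damage, but neither endpoint repairs the hospitalization and in-hospital death figures.

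Finally, a 30-day all-cause window is reproducible and could be kept under an honest label. That is also fair; the conflict is with the label in Section 8.7.

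**Conclusion.** The concern holds in this form: the definition does not include day 0 or stays in progress at diagnosis, and read literally it excludes admissions during which influenza was first recorded. On every reading it is all-cause while being reported as influenza-related. In-hospital death inherits both faults. Severity is moderate. Only descriptive secondary endpoints are affected; the frequency and incidence of influenza and ILI, the primary endpoints, are untouched.

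A reader might infer more: that the plan demonstrably undercounts severe influenza, perhaps by a fifth to a half, and loses most in-hospital deaths. The documents do not support this. They give no share of influenza first diagnosed during a stay, no background admission rate and no distribution of deaths. The undercount also rests on a strict admission-date reading that the text does not impose, and the unrelated admissions push the other way. Size and net direction cannot be derived.

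The limitations in Section 8.9 do not cover the point. They warn that mild cases go unrecorded, not that inpatient-diagnosed cases may fall outside the hospitalization endpoint.

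**What to change.** Define influenza hospitalization as any inpatient stay whose admission-to-discharge interval contains the influenza diagnosis date, or that begins on day 0 to 30 after it. This captures cases 1 to 3 above and removes the dependence on how *post* is read.

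Report stays carrying an influenza or respiratory diagnosis separately from all-cause stays, and label the latter all-cause hospitalization after influenza. Case 4 then appears only in the all-cause line unless its stay carries such a code. Base in-hospital death on the same definition, with the same split. Put identical wording in the protocol table and the SAP, and bring the label in Section 8.7 into line.

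The cost is a changed variable definition and minor programming in data already held. The downside is that some patients admitted for another reason who acquire influenza in hospital will enter. The coded split separates them only in part, since their stays may carry an influenza code too, and the report should say so.

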RedactedRedactedRedactedRedactedRedactedRedactedRedactedRedacted
Redacted
Redacted

Additionally, the frequencies and incidence rates of influenza infection and influenza like illness, and the frequencies of influenza-related clinical outcomes, including mortality, will be reported by influenza season (annual datacut from 01 June – 31 May). Although there may be under-reporting and misclassification, presence of influenza vaccine in individual patient records will also be reported for each influenza season.

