8. RESEARCH METHODS

8.1. Study Design

This is a retrospective records-based cohort study involving secondary analysis of **Redacted** Electronic Health Record (EHR) databases in the US consisting of longitudinal health information about patients derived from participating healthcare provider organizations with details below.

This study period is 01 June 2014 through 31 May 2019. The June 2014 start date is intended to avoid potentially intractable channeling of patients with high unmet need into tofacitinib group given status as first in class to a new mechanism of action following US approval in November 2012.

This study first focuses on the whole study period (01 June 2014 through 31 May 2019), then perform frequency and incidence rate analysis for each influenza season (01 June through 31 May the next year).

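### The 31 May cut-offs conflict with the 90-day death and 30-day outcome windows; if outcome capture stops at the cut, late-season outcomes are undercounted

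*Supplement*

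**What the plan says.** Section 8.1 sets the calendar limits: "This study period is 01 June 2014 through 31 May 2019". After the whole-period analysis the plan will "then perform frequency and incidence rate analysis for each influenza season (01 June through 31 May the next year".

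The paragraph on by-season reporting that precedes Section 8 covers influenza and ILI frequencies and rates, and also the frequencies of clinical outcomes including mortality. All of these "will be reported by influenza season (annual datacut from 01 June – 31 May".

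Section 8.3 ties the secondary outcomes to the influenza diagnosis date:
- death: "Death within 90 days post influenza diagnosis";
- hospitalization: "hospitalization within 30 days post influenza diagnosis";
- complications, for example "Clinical diagnosis of pneumonia on or up to 30 days after an influenza diagnosis", with the same window for stroke or MI and for neurological disorder;
- concomitant medication, for example "Corticosteroid use within 30 days [-30,30] around an influenza diagnosis".

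Section 8.7 reports complications, hospitalization and mortality as frequencies. It states no rule for censoring or for incomplete windows. Section 8.9 does not list incomplete outcome windows among the limitations.

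**The concern.** A 90-day window opened in late spring, or a 30-day window opened in May, extends past 31 May. The cut is attached to the outcomes, mortality among them, and not only to the influenza diagnoses. A programmer following the text literally could therefore stop looking for events on 31 May while keeping every diagnosis in the denominator. A death on, say, day 60 of a case diagnosed in April would then be counted as no death.

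An error of this kind goes in one direction only: case fatality and complication frequencies come out too low. Its size depends on how late the cases fall, so a late season would look milder than an early one. That would distort the season-by-season description the protocol sets out to give.

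**Working it through.** The documents give no mortality figure, event count or sample size to reproduce. The check is calendar arithmetic, followed by an illustrative loss calculation.

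**Step 1. Last diagnosis date with a complete window** (Sections 8.1 and 8.3; day 90 and day 30 counted as inside the window)

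- Death: 31 May − 90 days = 2 March. Windows are incomplete for diagnoses from 3 March to 31 May, which is 29 + 30 + 31 = 90 diagnosis days.
- 30-day outcomes: 31 May − 30 days = 1 May. Windows are incomplete for diagnoses from 2 May to 31 May, 30 diagnosis days. The forward half of the medication window has the same limit.
- These dates are the same in all five seasons.

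**Step 2. Which seasons are exposed**

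| How the cut is read | Seasons with incomplete windows |
|---|---|
| Cut assigns diagnoses to seasons; data run past 31 May 2019 | None |
| Cut assigns diagnoses to seasons; data end on 31 May 2019 | 2018-2019 only |
| Cut also ends outcome capture each year | All five |

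The study period has 1826 days. If only the last season is cut, the affected diagnosis dates are 90/1826 = 4.9% of the calendar for death and 30/1826 = 1.6% for 30-day outcomes. These are shares of days, not of cases.

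**Step 3. Share of 90-day deaths lost in a cut season**

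The documents give neither the seasonal distribution of diagnoses nor the timing of deaths, so both are assumptions. Let *q* be the share of the season's diagnoses in its last 90 days, spread evenly over those days. Let *r* = 0, …, 89 be the days left before the cut, and F(*r*) the share of 90-day deaths that occur by day *r*.

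Loss = *q* × (1 − mean of F(*r*))

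- Deaths uniform over 90 days: F(*r*) = *r*/90, and the mean is (0 + 1 + … + 89)/(90 × 90) = 4005/8100 = 0.494.
- Front-loaded deaths (exponential truncated at 90 days): F(*r*) = (1 − e^(−*r*/m))/(1 − e^(−90/m)). The mean is 0.713 for m = 30 days and 0.830 for m = 15 days.

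| Death timing | Lost among late diagnoses | *q* = 10% | *q* = 20% | *q* = 30% | *q* = 40% |
|---|---|---|---|---|---|
| Uniform | 50.6% | 5.1% | 10.1% | 15.2% | 20.2% |
| Exponential, m = 30 | 28.7% | 2.9% | 5.7% | 8.6% | 11.5% |
| Exponential, m = 15 | 17.0% | 1.7% | 3.4% | 5.1% | 6.8% |

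**Step 4. Pooled over the whole period**

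With five equal seasons and only the last one cut, divide by 5: from 1.7%/5 = 0.3% to 20.2%/5 = 4.0%.

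**Step 5. What the remedy needs**

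For a diagnosis on 31 May 2019, day 30 is 30 June 2019 and day 90 is 29 August 2019. Section 8.2.1 describes the source as "treating more than 103 million patients receiving care as of January 2020", which is later than both dates.

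**The case against.** The strongest reply is that nowhere does the text say outcome capture stops on 31 May. Section 8.3 gives influenza season the role of a stratifying variable and anchors every outcome to the diagnosis. The natural reading is then that diagnoses are sorted into seasons and each is followed for its stated window. For the first four seasons the 90 days after 31 May lie inside the study period. For the last season the source may well hold later data. Section 8.3 also leaves time periods to the SAP. Neither the SAP nor Section 8.2.2 was in the text reviewed, and either could contain the rule.

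Much of this stands. It rules out the stronger reading a reader might infer, that mortality is in fact understated and in every season; that holds only if the annual cut ends outcome capture. It also rules out treating 2018-2019 as affected in any case. Equally, the January 2020 description counts patients in care and does not give the end date of the study extract, so it cannot show that the last season is safe.

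The reply does not remove the point. The complaint is not that a definition is absent. The study end, the annual cut applied to outcomes and the outcome windows are all stated in the protocol, and taken together they do not fit. Section 8.8 has the analyses programmed from the protocol, with the SAP used where applicable, so the wording of the protocol matters.

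**Conclusion.** The concern holds as a conflict in the protocol's stated dates, with a conditional bias. If capture stops at the cut, 90-day death is incomplete for diagnoses from 3 March and the 30-day outcomes only from 2 May. It would be wrong to extend the March-to-May range to hospitalization and complications. Crude frequencies would be biased downward: about 2-20% of a cut season's 90-day deaths, or about 0.3-4% pooled if only the last of five equal seasons is cut. These figures rest on the assumed 10-40% late share, even spread of late diagnoses and assumed death timing. No size is put on the 30-day outcomes.

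A reader might also infer that treatment groups with more late-calendar follow-up would look safer. The documents give nothing with which to size that, and Section 8.9 disclaims inference about treatment.

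The affected endpoints are secondary and descriptive, and the primary influenza and ILI incidence rates are untouched. Severity is moderate: worth correcting before programming, but not a flaw that undermines the study.

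**What to change.** In Sections 8.1 and 8.3, state that each influenza diagnosis is assigned to a season by its diagnosis date, and that its outcomes are ascertained for the full 30 or 90 days even when these run past the season boundary. For 2018-2019, extend outcome look-up, but not case entry, to 29 August 2019 if the extract allows. Change the by-season paragraph so that the annual cut plainly governs diagnoses and not outcome capture.

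If the extract cannot be extended, restrict the 2018-2019 analysis, numerator and denominator alike, to diagnoses on or before 2 March 2019 for 90-day death and on or before 1 May 2019 for the 30-day outcomes. Say so in the tables and in Section 8.9.

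The first option costs a sentence or two and a later look-up date. The fallback costs cases. Under the assumption above, the 90-day measure loses 10-40% of the last season's diagnoses, or 10%/5 = 2% to 40%/5 = 8% of the total over five equal seasons. The 30-day measures lose only diagnoses made from 2 May 2019.
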